### 3. Abstract:

Proton Pump Inhibitors (PPIs) are indicated for the treatment of gastroesophageal reflux disease (GERD), *H. pylori* infection, peptic ulcer disease, and gastric protection in patients at risk for gastrointestinal bleeding. PPIs are among the most commonly prescribed drugs in the world, and their most common indication is GERD. Refractory GERD is the term used to describe non-responsiveness to conventional PPI therapy, and it occurs in up to 40% of patients even when the PPI dose is doubled. The efficacy of PPIs is highly dependent on plasma concentrations achieved following drug administration. All PPIs are metabolized in part by the *CYP2C19* enzyme, which is encoded by the highly polymorphic *CYP2C19* gene. Depending on the *CYP2C19* genotype, individuals are classified into different metabolizer phenotypes: poor metabolizers (PM, 2 loss-of-function *CYP2C19* alleles); intermediate metabolizers (IM, one loss-of-function allele); normal metabolizers (NM, no loss or gain-of-function alleles); rapid metabolizer (RM; one gain-of-function allele) and ultra-rapid metabolizers (UM, two gain-of function-alleles). Genetic variants in *CYP2C19* are known to profoundly influence PPI plasma concentrations and consequently, response to PPI therapy. For example, individuals classified as either RM or UM have lower PPI concentrations compared to NM, IMs, or PMs, respond poorly to PPI therapy, and some fail to respond even when the PPI dose is increased. **We hypothesize that genotype-supported treatment of GERD and dyspepsia will lead to better GERD control and improvement in severity of dyspepsia symptoms compared to conventional treatment.** We will conduct a comparative effectiveness study of genotype-supported vs. conventional treatment of GERD and dyspepsia. Patients presenting with GERD or dyspepsia symptoms and either 1) being initiated on PPI therapy or 2) with continued symptoms on current PPI therapy will be recruited from gastroenterology clinics and randomized to a genotype-supported versus conventional PPI therapy management strategy. We will integrate individual *CYP2C19* genotype information into treatment decisions for the genotype-supported arm and compare change in symptom control from baseline to the end of the study between study arms. Given that PPI efficacy is related to PPI exposure and to metabolizer phenotype, individualizing treatment using *CYP2C19* genotype information is expected to improve symptom

management. We will also evaluate patient and clinician knowledge, attitudes, and beliefs about pharmacogenetic testing and physician acceptance of genetic information into clinical practice. Finally, we will collect preliminary data on the potential impact of *CYP2C19*-supported PPI dosing on adverse event rates.

#### **4. Background:**

In the past 10 years, there have been significant advances in defining genetic determinants of drug response. These advances have led to the expectation by many that eventually an individual's personal genetic information will become part of his or her medical record to be used to guide treatment decisions. The UF Health Personalized Medicine Program (PMP) was created at UF to meet this expectation. The initial efforts of the PMP involved implementation of cytochrome P450 (CYP) 2C19 genotyping to guide antiplatelet therapy following percutaneous coronary intervention.

At UF Health, *CYP2C19* genotyping is available clinically. However, the gastroenterologists do not use *CYP2C19* genotype information, and there is a need for further evidence generation, which propose to do through a pilot implementation study. The proposed study is significant because it may extend the evidence regarding influence of *CYP2C19* genotype in PPI efficacy, lead to more rationale dosing of PPIs and management of patients with GERD or dyspepsia, and build a body of evidence to facilitate the implementation of pharmacogenetic-supported GERD and dyspepsia management.

**GERD Refractory to PPI Treatment.** Gastroesophageal reflux disease (GERD) affects 10-20% of individuals in Western countries. PPIs are agents of choice to treat GERD, and are among the highest-selling classes of drugs in the US, with \$9.5 billion in sales in 2015. Six PPIs are commercially available: omeprazole (Prilosec); lansoprazole (Prevacid), dexlansoprazole (Dexilant) esomeprazole (Nexium), pantoprazole (Protonix), and rabeprazole (Aciphex). Low doses of omeprazole and lansoprazole can be purchased over the counter. While effective for symptom relief and erosive esophagitis, PPI treatment fails in up to 40% of patients with GERD. Failure to respond to standard, once daily PPI treatment or complete or partial response to twice daily PPI treatment has been defined as refractory GERD. Several factors have been associated with refractory GERD, including adherence to PPI therapy, esophageal hypersensitivity and inter-individual differences in PPI metabolism^11.

***CYP2C19* genetic variation influences the pharmacokinetics of PPIs.** PPIs inhibit the final pathway of acid production in gastric parietal cells by covalently binding to the H+/K+-ATPase proton pump leading to inhibition of acid secretion, which lasts for 24-48 hours despite the drug's short pharmacokinetic half-life. Most PPIs are metabolized by CYP2C19 and CYP3A4; have short elimination half-lives (1-4 hours) and distribution volumes that are 8%-20% of total body water. All PPIs have low hepatic clearances, low first-pass metabolism and have high bioavailabilities. The *CYP2C19* gene that encodes the CYP2C19 enzyme is located on chromosome 10q24.1-q24.3, has 9 exons and is highly polymorphic.

Several loss of function alleles (e.g., *CYP2C19*\*2 through \*9) reduce drug clearance and significantly increase PPI plasma concentrations and area under the plasma concentration-time curve (AUC). Carriers of one or two loss of function alleles are referred to as intermediate and poor metabolizers (IMs and PMs), respectively. The extent to which

**CYP2C19** variation affects clearance depends on the fraction of total clearance attributable to CYP2C19. All PPIs undergo significant metabolism by CYP2C19, and genetic variation in CYP2C19 influences the pharmacokinetics of all PPIs. The G681A polymorphism causes a splicing defect in exon 5 resulting in protein synthesis termination and is responsible for the \*2 allele, the most prevalent LOF allele. The wild type (WT) CYP2C19\*1 allele is the nomenclature assigned when no functional variant alleles are present, and is associated with a more rapid clearance and lower AUCs compared to the PM or IM phenotypes.

Those who are homozygous for \*1 are referred to as and are responsible for normal metabolizers (NM). CYP2C19\*17 is a gain- of-function allele that increases the clearance of PPIs and reduces AUC compared to NMs. The \*1/\*17 or \*17/\*17 genotypes contribute to the rapid or ultra-rapid metabolizer phenotype (RM or UM, respectively). The AUC following the administration of equal PPI doses can vary 3-10 fold between PMs and UMs. Table 1 shows population frequency data for the various genotypes/inferred phenotypes from the UF clinical implementation of CYP2C19 genotyping for clopidogrel response prediction.

**TABLE 1. CYP2C19 genotypes, inferred phenotypes, and population frequencies**

ALLELE a	GENOTYPE/ACTIVITY	PHENOTYPE b	FREQUENCY
*1/*1	Wild Type (WT)/ 2 active alleles	NM	39%
*1/*n	Heterozygous WT/1 active, 1 LOF allele	IM	20%
*2/*2 or *n/*n	Homozygous variant/2 LOF alleles	PM	1.7%
*1/*17	Heterozygous WT/1 active, 1 GOF allele	RM	28%
*17/*17	Homozygous variant/2 GOF alleles	UM	5.3%
*2/*17	Heterozygous; 1 LOF/ 1 GOF allele	?	5.6%

a \*2, \*3, \*8, or \*9 refer to loss-of-function (LOF) alleles, n refers to any of the LOF alleles

b Abbreviations: GOF –gain of function; NM—normal metabolizer; IM – intermediate metabolizer; PM – poor metabolizer; RM—rapid metabolizer; UM—ultra-rapid metabolizer

#### Efficacy of PPIs depends on plasma concentrations and CYP2C19 genetic variation.

Studies report that the efficacy of PPIs to treat GERD and related conditions is closely linked to plasma concentrations. Numerous studies in adults have shown that CYP2C19 variants markedly influence the pharmacokinetics and pharmacodynamics of PPIs (see reviews). *H pylori* cure rates are significantly higher among PMs compared to RMs, and higher doses of PPI are required to treat *H pylori* in RMs.

Long-term PPI use is associated with increased risk of adverse events. Use of PPIs has increased dramatically in the last decade, driven in part by an impression that they are “benign drugs”. As a result they are often prescribed as long term therapy in multiple different patient populations. It is not uncommon for patients to be on PPI therapy for multiple years or even “indefinitely”, despite no clear indication being present. However, there is mounting evidence that long-term use of PPIs are associated with a number of significant adverse effects including gastric and respiratory infections, bone fractures and kidney disease. For example, studies have reported increased risk of intestinal infections with *Salmonella*, *Clostridium difficile*, *Shigella*, *Campylobacter*, *Streptococcus*, *Lactobacilli* and fungus with PPI use (see reviews). This is believed to be due to reduced effectiveness of the pH barrier in the stomach to protect against infections from ingested bacteria and viruses with chronic gastric acid suppression. If aspirated during reflux episodes, infected gastric media may increase the risk of upper respiratory infections. Several studies have reported associations between the chronic use of PPIs and upper respiratory infections and community-acquired pneumonia. PPI use has also been associated with bone fractures in young adults. Recent studies have also

linked PPI use with the risk of chronic kidney disease (CKD) and with progression to end-stage renal failure (ESRD). Additionally, there is evidence suggesting that higher daily PPI doses and/or the degree of acid suppression increase risk for PPI-associated adverse effects, thereby supporting a role for *CYP2C19* genetic variation contributing to adverse events. While the primary focus of this proposal is the impact of *CYP2C19* genotype-supported management of GERD and dyspepsia, we will also collect follow-up data on the occurrence of gastrointestinal and pulmonary/upper respiratory infections, bone fracture, and adverse kidney outcomes to begin building evidence on whether genotype-supported treatment of GERD and dyspepsia may influence risk for adverse outcomes.

This study is significant because it will prospectively test the hypothesis that genotype-supported treatment in patients with GERD and/or dyspepsia leads to better symptom control compared to conventional treatment. Data on adverse events with *CYP2C19*-supported treatment gained from this study will be used to inform power calculations for a larger study focused on preventing PPI-associated adverse events through genotype-supported dosing.

Table 2. Comparison of lansoprazole plasma concentrations by *CYP2C19* phenotype.

Phenotype	Alleles	Number Participants	Mean $\pm$ LZ Con. ng/ml
NM	*1/*1	11	199 $\pm$ 137
IM	*1/*2 or *3	13	303 $\pm$ 165
RM	*1/*17	11	168 $\pm$ 146
UM	*17/*17	2	156 $\pm$ 123
?	*2/*17	4	201 $\pm$ 57.1

A companion study in children will be conducted at Nemours Children's Hospital Gastroenterology Clinics in Orlando. The preliminary data below were generated by investigators at Nemours and helped to inform sample size calculations for our study.

## 5. Preliminary Data

Lansoprazole pharmacokinetic data and *CYP2C19* genotype. Table 2 demonstrates the relationship between plasma drug concentrations (AUC) and *CYP2C19* genotype.

The data in Table 2 were collected from children with asthma taking a 30-mg lansoprazole (LZ) dose daily for 6 months. Blood was drawn 2 hours after the final dose, which corresponds to time at which blood levels peak after an oral dose. Note that compared to individuals with the NM phenotype, LZ concentrations were higher in carriers of one loss-of-function allele (\*1/\*2 or \*3; IM) indicating decreased clearance. Carriers of \*17 gain-of-function allele (RM) had lower LZ concentrations compared to NMs or PMs, indicating higher clearance. Though the number of participants is small, \*17/\*17 participants (UMs) had the lowest LZ concentrations; and for \*2/\*17 participants levels were similar to \*1/\*1 alleles (NM phenotype). These preliminary data support the hypothesis that *CYP2C19* variations influence the PK of LZ in children and that *CYP2C19* genotype can be used to discriminate metabolizer phenotypes.

Association Between *CYP2C19* Phenotype and pH Testing Outcomes in Children taking PPIs. Esophageal pH probe testing is commonly performed in children to assess the efficacy of PPI medication therapy for GERD. We hypothesized that the *CYP2C19* gain-of-function genotype among children who have undergone esophageal pH probe testing while

on PPI therapy would be associated with pH probe acid exposure outcomes. Tissue collected during pH probe testing was genotyped in 74 children using Taq Man techniques. Children with the RM phenotype (gain-of-function genotype) had a poorer response to PPI (e.g. had more time with pH <4) compared to PM and NM phenotypes (Table 3). Our data support that *CYP2C19* variants influence response to PPI and suggest that genotype-supported PPI dosing may avoid pH probe testing in some children. We also hypothesize the same would be observed in adults.

Comparison of *CYP2C19* SNP Frequencies in Controls vs. Children Undergoing Fundoplication.

Table 4 shows *CYP2C19* \*2 (loss-of-function) and \*17 (gain-of-function) allele frequencies in children who were on PPIs and underwent fundoplication surgery compared to controls (consisting of asthmatic patients who participated in the PPI trial). DNA for genotyping was obtained from saliva samples collected from controls, and for cases was obtained from tissue samples collected from children during fundoplication surgery. The frequency of the

CHARACTERISTIC	GOF (N=21)*	LOF (N=53)	RR (CI)	P value
Caucasian, %	76	71		NS
Male, %	66	62		NS
Mean Age at pH test, years(SD)	8(4.6)	8(4.9)		NS
Mean PPI Dose(SD), mg/kg	1.26(0.45)	1.00(0.62)		NS
% time pH < 4	5.71	2.67	1.6 (1.1-2.3)	<0.005
Mean Acid clearance (SD)	181(271)	107(158)	2.2 (1.5-3.2)	<0.0001
Mean Number Acid Reflux	25(35)	24(32)	0.71-1.5	NS
Episodes(SD) in 24 hrs				

\*GOF = Gain-of-function--\*17 carriers, LOF = Loss-of-function carriers + no variant alleles

minor \*2 allele (A allele in Table 4) (PM or IM phenotype) was under-represented in the fundoplication cohort compared to controls, and the minor allele for the \*17 allele (T allele) (RM phenotype) was over-represented in the fundoplication cohort compared to controls. These data suggest that RMs are more likely to be undertreated with usual doses of PPI therapy and as a result are subjected to invasive management approaches. In contrast those with the PM phenotype are effectively treated with a usual dose and so are under-represented in the surgical group. These data could be inferred to suggest that genotype-supported PPI dosing could result in dose increases in RMs, which may have the potential to reduce the number of children who would need to undergo fundoplication surgery.

SNP/GENOTYPE	CONTROL 	FUNDOPLICATION
*2 (rs4244285)	Number (Percent)	Number (Percent)
GG	199 (71.5%)	31 (91.2%)
GA	75 (27.0%)	3 (8.8%)
AA	4 (0.15%)	
MAF	0.149	0.044
p value		0.010
*17 (rs12248560)		
CC	178 (64.0%)	17 (50%)
CT	91 (32.6%)	14 (41%)
TT	10 (3.50%)	3 (9.0%)
MAF	0.200	0.294
p value		0.033

Collectively, these preliminary data provide compelling evidence for the potential clinical utility of *CYP2C19*-genotype supported dosing by documenting 1) the relationship between *CYP2C19* genotype and PPI pharmacokinetics, 2) that response to PPI therapy, based on gastric pH, is influenced by *CYP2C19* genotype, and 3) that patients are undergoing risky, invasive procedures who may simply need a higher dose of PPI to overcome their RM phenotype status.

## 6. Specific Aim:

**Implement pharmacogenetic testing of the *CYP2C19* gene-PPI drug pair in the context of a comparative effectiveness genotype-supported vs. conventional treatment trial.** Given that PPI efficacy is related to PPI exposure and to metabolizer phenotype, individualizing treatment using *CYP2C19* genotype-supported dosing is expected to improve symptom control. **We hypothesize that genotype-supported treatment of GERD and dyspepsia will lead to better GERD control and improvement in the severity of dyspepsia symptoms compared to conventional treatment.** We will also survey patients and clinic staff on knowledge, attitudes, and beliefs toward pharmacogenetic testing, evaluate physician acceptance of genetic information into clinical practice, and collect preliminary data from the electronic health records on the potential impact of *CYP2C19*-supported treatment on the adverse event rate of upper respiratory infection (cold), sore throat, strep throat, bronchitis, pneumonia, ear infection, acute sinusitis (sinus infection), bone fractures, renal function, and gastrointestinal infections.

## 7. Research Plan:

The study is a randomized, open-label, comparative effectiveness clinical trial in 180 total patients with GERD or dyspepsia symptoms who will be randomized to either conventional or genotype-supported treatment of GERD and dyspepsia. A total of 120 patients will be enrolled in the UF Health Gastroenterology Clinics in Gainesville, and 60 will be enrolled in a parallel study (under separate IRB protocol) at Nemours Children's Hospital Gastroenterology Clinics in Orlando, FL. Each site will be responsible for overseeing patient care and research at their respective facility. All participants will have symptoms of GERD or related diseases and be candidates for PPI therapy or on PPI therapy with continued symptoms.

We will enroll a total of 180 patients between the UF Health and Nemours sites, which should allow for sufficient power to detect our efficacy endpoint (see power calculation below). We will also collect data from the health records for up to 24 months after enrollment on upper respiratory infection (cold), sore throat, strep throat, bronchitis, pneumonia, ear infection, acute sinusitis (sinus infection), bone fractures, renal function, and gastrointestinal infections for preliminary assessment of the effects of *CYP2C19*-supported PPI dosing on adverse effects. This exploratory arm will provide data to inform power calculations for a larger study focused on preventing PPI-associated adverse events through genotype-supported dosing.

**Inclusion Criteria.** A total of 120 patients with GERD or related symptoms will be enrolled at UF Health. An additional 60 patients will be enrolled at Nemours Children's Hospital Gastroenterology Clinics under a separate IRB protocol. For this protocol, any patient over the age of 17 who presents to GI clinic with GERD or related symptoms and is either 1) being initiated on PPI therapy or 2) continues to have symptoms despite PPI therapy will be considered eligible for the study.

Exclusion Criteria. This study will exclude patients who have had extensive esophageal or gastric surgery or any major chronic illness or condition that in the opinion of the gastroenterologist that would interfere with participation in the study.

Participant Recruitment Methods.

Prior to enrolling their patients, clinicians at participating GI clinics (investigators for this study) will be asked to complete surveys that assess their knowledge, attitudes, and beliefs as they relate to pharmacogenetics testing.

Patients will be approached for participation at their GI clinic visit by the treating clinician and/or physician assistant. After providing informed consent, patients will be randomly assigned to either conventional treatment or genotype-supported PPI therapy using a randomization table. A 5-ml (one teaspoon) venous blood sample will then be drawn by a nurse, physician assistant, or phlebotomist. The patient will be asked to complete 3 surveys/questionnaires: the Reflux Disease Questionnaire (RDQ), Global Overall Symptom (GOS) scale, and a survey to assess knowledge, attitudes, and beliefs about pharmacogenetic testing. Patients will receive a total of \$25 for participating in this study. The \$25 VISA gift card will be provided after completing the final questionnaire. Patients in the control group may be withdrawn prior to completion if they or their physician elect to order the genetic test during the study. These patients would receive a \$10 VISA gift card for their participation up to the point of withdrawal.

Genotyping and result reporting. Genotyping will be done by the CLIA-licensed UF Pathology Laboratory, as has been done for over 1,600 patients in the UF Health CYP2C19-clopidogrel implementation, with genotype results reported in the EHR. For patients randomized to the genotype-supported arm, genotype results will be available in approximately 2 weeks. For patients randomized to the conventional treatment arm, the genotype results will be resulted in the EHR after the patient completes study participation (12 weeks after patient enrollment). The patient's clinician will be educated about the genotype results and their implication for PPI response. A recommendation for a dose increase will be provided for RMs and UMs (approximately 30% to 35% of patients). For patients with other genotypes, clinicians will be advised that usual PPI doses are expected to be effective that lower doses may be sufficient for symptoms management in PMs. Clinicians will also be provided quick reference guides that will include phenotype, genotype, dosing recommendations, and educational information. The PMP Committee has convened with the GI clinicians to evaluate and approve the dosing recommendations for adults based on CYP2C19 genotype. Clinical decision support tools in the EMR will also be implemented that will provide this guidance to the treating clinician. While dosing recommendations will be provided based on genotype results, the ultimate prescribing decision will be left to the discretion of the treating physician.

Assessment of PPI efficacy and adverse effects. Our primary outcome will be the effectiveness of PPI therapy, which will be determined via two questionnaires: RDQ and GOS scale, administered by study personnel at baseline and 12 weeks. The RDQ was developed to monitor treatment response over time and evaluates 6 symptoms (12 items) covering 3 domains: heartburn, regurgitation, and upper abdominal pain. Each symptom is evaluated using a 6-point Likert scale to assess frequency and severity over the previous week. Each symptom is rated from 1 (did not have) to 6 (severe), and the RDQ mean score is calculated as the mean response to the 12 items. The RDQ mean score thus ranges from 1 to 6 and has been psychometrically validated. The GOS scale evaluates 18 symptoms, with each rated from 1 (no problem) to 7 (very severe). Similar to the RDQ, the mean score is calculated as the mean response to the 18 items, with mean scores ranging from 1 to 7. Patient participation will end after they complete the approximate 12 week questionnaire. However, we will continue to

follow patients over 24 months through medical record review to assess adverse outcomes for occurrence of upper respiratory infection (cold), sore throat, strep throat, bronchitis, pneumonia, ear infection, acute sinusitis (sinus infection), bone fractures, renal function and gastrointestinal infections.

Metrics for assessing success of pharmacogenetic testing in clinical practice. We will test a variety of variables that will provide insight into attitudes and acceptability of pharmacogenetic testing. These will include: 1) percent of patients approached about the study who agree to participate; 2) surveys of patients and clinic staff on knowledge, attitudes, and beliefs about pharmacogenetic testing; and 3) the percent of the time a dosing recommendation for a patient in the genotype-supported arm is accepted by the clinician. Patients will be surveyed about knowledge, attitudes, and beliefs about pharmacogenetic testing using questionnaires on enrollment and at the end of their study participation. Clinic staff will be surveyed about knowledge, attitudes, and beliefs about testing at the beginning and end of the study.

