### **Analysis Plan and Power Calculations:**

We will test the hypothesis that RMs/UMs (1 or 2 gain-of-function alleles) in the genotype-supported arm have better GERD and symptom control than RMs/UMs in the conventional treatment group because they will have their dose increased based on their genotype.

Continuous variables will be compared between the genotype-supported group and the conventional treatment group using the Student's unpaired *t*-test, and categorical variables will be compared using the chi-square or Fisher's exact test. The hypotheses will be tested using linear regression analysis to estimate the difference in the RDQ reduction in the RM/UM patients between the two arms. All analysis will be performed in SAS 9.4 (Cary, NC).

We will evaluate the percentage of the time when a dosing recommendation was made and accepted by the treating clinician, to provide practical data on the willingness of clinicians to adopt this approach. We will also collect patient- and provider-level survey data on knowledge, attitudes, and beliefs about pharmacogenetics testing, using survey tools adapted from other IRB-approved studies.

Power calculation. While there are no data in the literature on genotype associations with the efficacy endpoint we will use (symptom improvement), there are pH probe data by genotype that were generated by the Nemours investigators, that we can use, and this should be an excellent surrogate for symptom data. We have done power calculations based on two of the pH-based response phenotypes, found in Table 3. Specifically we powered based on percent time with pH < 4 (which has an effect size of 0.79) and acid clearance time (effect size of

0.45). Based on these two phenotypes, we have the following power to detect differences in efficacy between *CYP2C19\*17* carriers and non-carriers:

Based on the previous data for acid clearance time, with 180 total participants (120 from UF Health and 60 from Nemours), we have 81% power to detect a 0.49 effect size.

Based on the previous data for time with pH <4.0, with 180 participants, we have >99% power to detect a 0.79 effect size.

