With 180 total patients (90 patients in each arm), we expect approximately 30 patients in each arm to have the genotype of interest (i.e. RM or UM). At alpha of 0.05, we will have 80% power to detect effect size of  $\geq 0.74$  in the RDQ score in RMs/UMs. This effect size is equivalent to a RDQ score difference of 1.22 for regurgitation and a score difference of 0.93 for heart burn. These differences in RDQ scores are smaller than what is considered clinically significant. Therefore our study is well-powered.

In summary, by studying a total 180 patients (120 from UF Health and 60 from Nemours), the data suggest we will have excellent power to detect an efficacy endpoint. Data generated from this protocol on adverse effects will also help us define the incidence of the adverse effect phenotypes to inform sample size for a future pragmatic trial examining effects of genotype-supported dosing on PPI safety endpoints.

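### The RDQ comparison ignores whether a patient is starting a PPI or is symptomatic on one, which loses precision and leaves the result in each setting unreported

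*Combined protocol and SAP*

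**What the plan says.** Under Inclusion Criteria in section 7 (Research Plan), an adult is eligible who "is either 1) being initiated on PPI therapy or 2) continues to have symptoms despite PPI therapy". The expected share of each route is not given.

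Under Participant Recruitment Methods, consenting patients are "randomly assigned to either conventional treatment or genotype-supported PPI therapy using a randomization table". No stratification factor is named. Blood for genotyping is drawn after assignment, and results take about two weeks in the genotype-supported arm.

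The RDQ looks back over the previous week and is administered at baseline and at 12 weeks (Assessment of PPI efficacy and adverse effects). The Analysis Plan tests the efficacy hypothesis by "linear regression analysis to estimate the difference in the RDQ reduction in the RM/UM patients between the two arms". It lists no covariate, subgroup or interaction for PPI status at entry.

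The only sentence on covariate adjustment is in the Statistical analysis paragraph of the Nemours part. It belongs to the logistic and Cox models there, selects covariates by significance, and does not name PPI status.

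**The concern.** The outcome is a change score, and the two routes start from different places. A starter's baseline precedes the newly started drug, so the 12-week fall contains the response to starting it, in both arms. A patient who is symptomatic on a PPI has a baseline measured on treatment. The expected RDQ fall can therefore differ by route whatever the arm. Baseline RDQ is not a substitute for route, because the same score can be a pre-treatment value in one patient and an on-treatment value in another.

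The effect of a genotype-prompted change could also differ by route. The Background ties refractory GERD to adherence and esophageal hypersensitivity as well as to metabolism.

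Two things are at stake. The first is precision, in a subset that is already small. The second is what the trial can say about its two entry settings, since no result is planned for either.

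**Working it through.** **The plan's own figure.** The power text says "With 180 total patients (90 patients in each arm"), and then "we expect approximately 30 patients in each arm to have the genotype of interest (i.e. RM or UM"). It continues: "At alpha of 0.05, we will have 80% power to detect effect size of" 0.74 or more. With 30 per arm, a standardized difference of 0.74 and two-sided alpha 0.05, a two-sample t-test has 80.5% power (normal approximation 81.8%). The plan does not state sidedness; one-sided alpha would give 88.9%, so two-sided is the match. The stated 80% reproduces.

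**Number per arm.** If only the UF adults supply the RDQ, there are 120/2 = 60 per arm, of whom about one third, or 20, are RM/UM. The Nemours part does not list the RDQ among its instruments. Power for 0.74 at 20 per arm is 63%.

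**SD.** The plan adds: "This effect size is equivalent to a RDQ score difference of 1.22 for regurgitation and a score difference of 0.93 for heart burn". The implied SDs are 0.93/0.74 = 1.26 and 1.22/0.74 = 1.65. These belong to domain scores, not to the 12-item mean, and serve here as proxies.

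**Assumptions not in the documents.** The starter share is p = 0.5, which gives the largest variance. The starter-minus-symptomatic difference in mean RDQ fall is D = 1.0 (range 0.5 to 1.5). There is no dropout.

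**Share of variance due to route** = p(1−p)D²/SD², reading the SD as the total SD:

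| D | SD 1.26 | SD 1.65 |
|---|---|---|
| 0.5 | 0.0625/1.588 = 4% | 0.0625/2.72 = 2% |
| 1.0 | 0.25/1.588 = 16% | 0.25/2.72 = 9% |
| 1.5 | 0.5625/1.588 = 35% | 0.5625/2.72 = 21% |

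**Power for a 0.93-point difference at 30 per arm, D = 1.0.**

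- If 1.26 is the total SD: the unadjusted analysis has about 80%. The residual SD after adjustment is √(1.588 − 0.25) = 1.16. Power rises to about 86%, allowing for the lost degree of freedom and chance correlation between route and arm.
- If 1.26 is the within-route SD: the unadjusted SD is √(1.588 + 0.25) = 1.36 and power is about 74%. Adjustment restores about 80%.

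**Chance imbalance in starter share.** Its SD is √(2p(1−p)/n), which is 0.129 at n = 30 and 0.158 at n = 20. The 95% ranges are ±25 and ±31 percentage points. The shift in the estimated arm difference is the imbalance times D:

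| D | 95% shift, 30 per arm | 95% shift, 20 per arm |
|---|---|---|
| 0.5 | ±0.13 | ±0.16 |
| 1.0 | ±0.25 | ±0.31 |
| 1.5 | ±0.38 | ±0.47 |

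Cancelling a true 0.93 would need an imbalance of 0.93/1.0 = 93 points at D = 1.0, or 0.93/1.5 = 62 points at D = 1.5. Both lie far outside the 95% range. Simulated type I error of the unadjusted test at 30 per arm was 4.8% to 5.1% for D from 1.0 to 2.0.

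**Stratifying the table.** Route is known at assignment but genotype is not, so stratification balances all patients rather than the RM/UM third that is analysed. If genotype is independent of route, the SD of imbalance in that subset falls by a factor of √(1 − 1/3) = 0.816: from 0.129 to about 0.105 at 30 per arm, and from 0.158 to about 0.129 at 20.

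**Reading by route.** An even split of 30 gives 15 per arm per route. Power for 0.74 SD is then about 50%, and the effect detectable with 80% power is 1.06 SD. Power for an arm-by-route interaction of 0.74 SD is about 30%.

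**The case against.** The strongest reply is that chance imbalance in a prognostic factor is ordinary sampling error. The standard error already carries it, type I error is held, and any drug response common to both arms cancels on average. If 1.26 is the total SD, the stated 80% power stands and adjustment is purely a gain. All of this is correct. Broad entry also suits a comparative-effectiveness pilot. What remains is that a readily available gain is left unused, and that nothing is planned by route.

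A reader might infer more, but the documents do not support it:

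- *Imbalance could swamp the dose effect.* At D = 1.0 and 30 per arm, the 95% shift of 0.25 is 27% of the planned 0.93 and 21% of 1.22. It would rival only a much smaller true effect than the one planned for.
- *The pooled answer fits neither group.* The pooled contrast is a valid average over the enrolled mix. It would mislead only if the effect differs by route, which the documents do not establish.
- *A starter's fall contains the whole first-time drug effect, and only dose can move the other group.* Being initiated on a PPI does not mean never having taken one, and the Background notes over-the-counter supply. Adherence, which the Background names as a factor, can also change over 12 weeks.
- *The Abstract's statement on refractory GERD, "it occurs in up to 40% of patients even when the PPI dose is doubled", shows that patients already failing will not respond.* That figure describes how often refractory GERD occurs, not the failure rate among those already failing.

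The size of the gain also depends on undocumented inputs. A less even mix, or the larger implied SD, makes it smaller.

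**Conclusion.** The point holds as a matter of precision and reporting, not of bias. The two entry routes are pooled, and nothing in the randomization or in the RDQ analysis accounts for them. For D between 0.5 and 1.5, route would explain about 4 to 35% of the variance at SD 1.26, or 2 to 21% at SD 1.65. At D = 1.0, SD 1.26 and 30 per arm, adjustment is worth about 6 percentage points of power on either reading of the SD. These sizes rest on the assumed 50:50 mix, the assumed D, and SDs taken from domain scores. That the plan omits entry route rests on none of them. It is a worthwhile improvement and does not threaten the validity of the test.

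**What to change.** Record PPI status at entry (being started, or symptomatic on a PPI) as a baseline variable; eligibility already requires it to be established. Name it in the Analysis Plan as a prespecified fixed factor in the linear regression of RDQ reduction in RM/UM patients. The cost is one recorded binary item and one degree of freedom.

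Report the RM/UM arm difference with its confidence interval for each route, labelled descriptive. State its imprecision alongside: about 50% power for 0.74 SD at 15 per arm, and less if the routes are uneven or only the UF adults contribute.

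If enrolment is still open, a separate randomization list per route is a reasonable option, at the cost of maintaining a second list. It only partly balances the RM/UM subset, so it supplements the model term and does not replace it. If enrolment has begun, the model term and the descriptive split are enough.
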